### **Criteria for Rechallenge of Amgen Investigational Product and Other Protocol-required Therapies After Potential Hepatotoxicity**

The decision to rechallenge the subject is to be discussed and agreed upon unanimously by the subject, investigator, and Amgen.

If signs or symptoms recur with rechallenge, then Amgen investigational product and other protocol-required therapies, as appropriate is to be permanently discontinued. Subjects who clearly meet the criteria for permanent discontinuation (as described in [Table 11-3](#)) are never to be rechallenged.

## Drug-induced Liver Injury Reporting and Additional Assessments

### Reporting

To facilitate appropriate monitoring for signals of DILI, cases of concurrent AST or ALT and TBL and/or INR elevation, according to the criteria specified in the above, require the following:

- The event is to be reported to Amgen as a serious adverse event immediately and no later than 24 hours of discovery or notification of the event (ie, before additional etiologic investigations have been concluded)
- The appropriate case report form (CRF) (eg, Events CRF) that captures information necessary to facilitate the evaluation of treatment-emergent liver abnormalities is to be completed and sent to Amgen

Other events of hepatotoxicity and potential DILI are to be reported as serious adverse events if they meet the criteria for a serious adverse event defined in Section [11.4](#).

### Additional Clinical Assessments and Observation

All subjects in whom investigational product(s) or protocol-required therapies is/are withheld (either permanently or conditionally) due to potential DILI as specified in [Table 11-3](#) or who experience AST or ALT elevations  $> 3 \times$  upper limit of normal (ULN) or 2-fold increases above baseline values for subjects with elevated values before drug are to undergo a period of “close observation” until abnormalities return to normal or to the subject’s baseline levels.

Assessments that are to be performed during this period include:

- Repeat AST, ALT, ALP, bilirubin (BIL) (total and direct), and INR within 24 hours
- In cases of TBL  $> 2 \times$  ULN or INR  $> 1.5$ , retesting of liver tests, BIL (total and direct), and INR is to be performed every 24 hours until laboratory abnormalities improve

Testing frequency of the above laboratory tests may decrease if the abnormalities stabilize or the investigational product(s) or protocol-required therapies has/have been discontinued AND the subject is asymptomatic.

Initiate investigation of alternative causes for elevated AST or ALT and/or elevated TBL.

The following are to be considered depending on the clinical situation:

- Complete blood count with differential to assess for eosinophilia
- Serum total immunoglobulin (Ig)G, anti-nuclear antibody anti-smooth muscle antibody, and liver kidney microsomal antibody-1 to assess for autoimmune hepatitis
- Serum acetaminophen (paracetamol) levels

- A more detailed history of:
  - Prior and/or concurrent diseases or illness
  - Exposure to environmental and/or industrial chemical agents
  - Symptoms (if applicable) including right upper quadrant pain, hypersensitivity-type reactions, fatigue, nausea, vomiting and fever
  - Prior and/or concurrent use of alcohol, recreational drugs and special diets
  - Concomitant use of medications (including non-prescription medicines and herbal and dietary supplements), plants, and mushrooms
- Viral serologies
- Creatine phosphokinase, haptoglobin, lactate dehydrogenase and peripheral blood smear
- Appropriate liver imaging if clinically indicated
- Appropriate blood sampling for pharmacokinetic analysis if this has not already been collected
- Hepatology consult (liver biopsy may be considered in consultation with a hepatologist)

Follow the subject and the laboratory tests (ALT, AST, TBL, INR) until all laboratory abnormalities return to baseline or normal or considered stable by the investigator. The "close observation period" is to continue for a minimum of 4 weeks after discontinuation of all investigational product(s) and protocol-required therapies.

The potential DILI event and additional information such as medical history, concomitant medications and laboratory results must be captured in the corresponding CRFs.

**11.8 Appendix 8. Eastern Cooperative Oncology Group (ECOG) Performance Score**

Grade	ECOG
0	Fully active, able to carry on all pre-disease performance without restriction.
1	Restricted in physically strenuous activity but ambulatory and able to carry out work of a light or sedentary nature, eg, light housework, office work.
2	Ambulatory and capable of all self-care but unable to carry out any work activities. Up and about more than 50% of waking hours.
3	Capable of only limited self-care, confined to bed or chair more than 50% of waking hours.
4	Completely disabled. Cannot carry on any self-care. Totally confined to bed or chair.

## 11.9 Appendix 9. Activity Measurements

**Table 11-4. Response Categories Based on Assessment of Target Lesions**

	Complete Response	Partial Response	Stable Disease	Progression of Disease
Measurable lesions	
 
Disappearance of all target lesions. Any pathological lymph nodes (whether target or non-target) must have reduction in short axis to < 10 mm.
 
	
 
≥ 30% decrease in the sum of diameters of target lesions, taking as reference the baseline sum diameters.
 
	
 
Neither sufficient shrinkage to qualify for PR nor sufficient increase to qualify for PD, taking as reference the smallest sum diameters while on study.
 
	
 
≥ 20% increase in the sum of diameters of target lesions, taking as reference the smallest sum on study (this includes the baseline sum if that is the smallest on study).
 
The sum of diameters of target lesions must also demonstrate an absolute increase of at least 5 mm.
 
The appearance of 1 or more new lesions.
 

Non-measurable lesions	
 
Disappearance of all lesions.
 
	Not applicable	Not applicable	
 
Unequivocal progression of non-measurable lesions.
 
The appearance of 1 or more new lesions.
 

Bone lesions	
 
Disappearance of all lesions.
 
	Not applicable	Not applicable	
 
At least 2 new lesions on first post-treatment scan, with at least 2 additional lesions on the next scan (2+2 rule). 
 
If at least 2 additional new lesions are seen on the next (confirmatory) scan, the date of progression is the date of the first post-treatment scan, when the first 2 new lesions were documented.
 
For scans after the first post-treatment scan, at least 2 new lesions relative to the first post-treatment scan confirmed on a subsequent scan.
 
 
 

PSA	Not applicable	Not applicable	Not applicable	An isolated PSA increase is not sufficient for PD per PCWG3

PCWG3 = Prostate Cancer Working Group 3; PD = progressive disease; PR = partial response; PSA = prostate-specific antigen.

Source: Eisenhower et al, 2009; Scher et al, 2016.

**Table 11-5. Time Point Response: Subjects with Target ( $\pm$  Non-target) Disease**

Target Lesions	Non-target Lesions	New Lesions	Overall Response
CR	CR	No	CR
CR	Non-CR/Non-PD	No	PR
CR	Not evaluated	No	PR
PR	Non-PD or Not all evaluated	No	PR
SD	Non-PD or Not all evaluated	No	SD
Not all Evaluated	Non-PD	No	NE
PD	Any	Yes or No	PD
Any	PD	Yes or No	PD
Any	Any	Yes	PD

CR = complete response; NE = not evaluated; PD = progressive disease; PR = partial response; SD = stable disease.

Source: [Eisenhower et al, 2009](#).**Table 11-6. Time Point Response: Subjects with Non-target Disease Only**

Non-target Lesions	New Lesions	Overall Response
CR	No	CR
Non-CR/Non-PD	No	Non-CR/ Non-PD a
Not evaluated	No	NE
Unequivocal PD	Yes or No	PD
Any	Yes	PD

CR = complete response; NE = not evaluated; PD = progressive disease; SD = stable disease.

a Non-CR/non-PD' is preferred over 'stable disease' for non-target disease since SD is increasingly used as endpoint for assessment of efficacy in some trials so to assign this category when no lesions can be measured is not advised.Source: [Eisenhower et al, 2009](#).

## **11.10 Appendix 10. Specific Guidance for Cytokine Release Syndrome**

Cytokine release syndrome (CRS) is clinically defined and may have various manifestations. There are no established diagnostic criteria. Signs and symptoms of CRS may include:

- constitutional: fever, rigors, fatigue, malaise
- neurologic: headache, mental status changes, dysphasia, tremors, dysmetria, gait abnormalities, seizure
- respiratory: dyspnea, tachypnea, hypoxemia
- cardiovascular: tachycardia, hypotension
- gastrointestinal: nausea, vomiting, transaminitis, hyperbilirubinemia
- hematology: bleeding, hypofibrinogenemia, elevated D-dimer
- skin: rash

Subjects may be at an increased risk for CRS during the first few days following the initial injection or infusion of AMG 340. CRS may be life threatening or fatal. Injection or infusion reactions may be clinically indistinguishable from manifestations of CRS.

Throughout the treatment with AMG 340, monitor subjects for clinical signs (eg, fever, tachycardia, dyspnea, tremors) and laboratory changes (eg, transaminase increase) which may be related to CRS.

Grading and management of CRS should be performed according to the guidelines provided in Section [11.10](#) (based on the adopted grading system referenced in Lee et al, 2019).

Please also refer to the general guidance for re-start of injection or infusion after interruptions/delay/withholding and dose modifications in Section [6.2.2.4](#).

For grade 3 and 4 CRS, please also see Section [6.2.1.4.1](#) for dose-limiting toxicity (DLT) considerations. Fever reported outside the context of CRS will be graded per CTCAE version 5.

### 11.11 Appendix 11. Cairo-Bishop Clinical Tumor Lysis Syndrome Definition and Grading

Common Terminology Criteria for Adverse Events (CTCAE) version 5.0 classifies tumor lysis syndrome (TLS) in grade 3 (present), grade 4 (life threatening consequences; urgent intervention indicated) and grade 5 (death). Presence of TLS is not clearly defined by CTCAE version 5.0. Cairo and Bishop developed a system for defining and grading TLS based on Hande-Garrow classification of laboratory or clinical TLS (Coiffier et al, 2008). For this trial, the Cairo-Bishop classification will be used to define presence of TLS, ie, presence of laboratory TLS and clinical TLS (see [Table 11-8](#)) including grading.

Based on the Cairo and Bishop system, laboratory TLS is defined as any 2 or more abnormal serum values present within 3 days before or 7 days after initiation of treatment in the setting of adequate hydration (with or without alkalinization) and use of a hypouricemic agent ([Table 11-7](#)).

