#### **2.2.4.2.1      Cross-linking CD3 with PSMA on Tumors and Potential T-cell Mediated Toxicities**

Pasotuxizumab is a PSMA-targeting bispecific T-cell engager or BiTE therapy being developed for metastatic castrate-resistant prostate cancer (mCRPC). In a phase 1 study in patients with mCRPC refractory to standard therapy (N = 16), pasotuxizumab was reported to have an acceptable safety profile with decreased lymphocytes and infections as the most common adverse events grade  $\geq 3$  (Hummel 2019).

Results from a phase 1 trial of HPN424 (a tri-specific anti-PSMA T-cell activating therapeutic candidate) being developed for mCRPC, reported that in 7 patients one grade 3 CRS event was noted which resolved within 8 hours. Three patients reported grade 2 rigors or fevers that were clinically manageable (Bendell et al, 2020). Overall, HPN424 was considered well-tolerated with all 7 patients continuing on study and no dose-limiting toxicities (DLTs) observed.

To reduce the risk of central nervous system (CNS) **adverse events** and CRS, AMG 340 is engineered to have reduced in vitro cytokine release (Section 2.2.4). Additionally, AMG 340 carries mutations in the Fc region that prevent Fc mediated effector function. Importantly, the potential for antibody dependent cellular cytotoxicity mediated killing of T-cells has been eliminated thus preserving T-cell function and reducing toxicity towards T-cells. The affinity of AMG 340 for PSMA is also at least 25-fold stronger than for CD3, based on cell surface binding. The potential risks of off-tumor T-cell-mediated CNS toxicity and CRS are anticipated to be reduced.

Additionally, the Schedule of Activities (Section 1.3) is designed to monitor and risk mitigate other known toxicities associated with previous bispecific CD3/PSMA therapies that include infections, tumor lysis syndrome, neutropenia, elevated liver enzymes, and leukoencephalopathy.

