**Table 2-2. Key Safety Risk for AMG 340**

Safety Risk	Description
Identified Risk	
Cytokine release syndrome (CRS)	Signs and symptoms may include (but not limited to) the following: 

• constitutional – fever, rigors, fatigue, malaise

• neurologic – confusion, headache, mental status changes, dysphasia, tremors, dysmetria, gait abnormalities, seizure (refer to immune-effector cell associated neurologic syndrome [ICANS] guidance in Section 6.2.1.6.1.1)

• respiratory – dyspnea, tachypnea, hypoxemia

• cardiovascular – tachycardia, hypotension

• gastrointestinal – nausea, vomiting, diarrhea

• hepatic – transaminitis, hyperbilirubinemia

• hematology – thrombocytopenia, bleeding, hypofibrinogenemia, elevated D-dimer

• skin – rash

Potential Safety Concerns	
Tumor lysis syndrome	Signs and symptoms may include hyperkalemia, hyperphosphatemia, hyperuricemia, hyperuricosuria, and hypocalcemia, potentially causing lethal cardiac arrhythmias, seizures, and/or renal failure.
Gastrointestinal toxicities	Signs and symptoms may include nausea, vomiting, diarrhea, abdominal pain, gastrointestinal inflammation and ulceration; mostly associated with CRS.
Neurological toxicities	Signs and symptoms include confusional state, headache, dizziness, encephalopathy, tremor, aphasia, and syncope; mostly associated with CRS.

Clinical signs and symptoms of CRS will be continually monitored throughout the duration of the study and at the time points indicated in Schedule of Activities (Section 1.3). Refer to Table 6-6, and Sections 6.1.5, 6.2.1.6.1.1, and 11.10 for specific recommendations regarding the mitigation and management of the risk.

Coronavirus disease 2019 (COVID-19) infection may theoretically increase the signs and symptoms of CRS. Refer to Section 5.2 and section below for additional guidance related to COVID-19.

The key safety risks are described further in the AMG 340 IB.

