#### **6.2.1.2 Dose Priming**

Based on the nonclinical pharmacology of AMG 340, a lower rate of CRS is anticipated than with other T-cell-engaging bispecifics; however, based on the mechanism of action of AMG 340, the most likely DLT to occur is still CRS  $\geq$  grade 3. Cytokine release syndrome will be managed per Principal Investigator discretion and institutional guidelines (a guide for management of CRS is provided in [Table 6-6](#) if institutional guidelines have not been established). Definitions for adverse events, serious adverse events, and DLTs are provided in Section [8.4.6.1.1](#), [8.4.6.1.2](#), and [6.2.1.4.1](#), respectively.

If a grade  $\geq$  3 CRS event occurs in Cohort N (where N represents a Cohort number) during the DLT period, or at the discretion of the DLRT, a dose equal to or less than the dose for Cohort N will be designated as the ‘Priming Dose’ and dose administration in subsequent cohorts (Cohorts N+1 and on) may be modified as follows:

- On Cycle 1 Day 1, subjects will receive the Priming Dose.
- On Cycle 1 Day 8, subjects will receive the full dose corresponding to the cohort in which they have been enrolled.

Note: a second priming dose may be introduced based on emerging data.

If a subject experiences CRS grade  $\geq$  2, or any other grade  $\geq$  2 toxicity after receiving a priming dose that is not unequivocally due to the subject’s underlying malignancy or other extraneous cause, administration of the full dose on cycle 1 day 8 must await approval by the Amgen Medical Monitor(s). At a minimum, CRS must have resolved to

grade  $\leq$  1 before the next is administered. The dose and timing of the full dose for such a subject may be modified at the discretion of the Amgen Medical Monitor and the Investigator; if the subject has their full dose reduced in cycle 1, the subject will be considered DLT-unevaluable and should be replaced. In subsequent cycles, subjects will receive the full dose on day 1.

Following implementation of a priming dose, if administration of the full dose is delayed in cycle 1, the DLT period for that subject should be extended to the same degree (eg, if the full dose is delayed by 4 days, the DLT period will also be extended 4 days). For clarity, treatment-emergent adverse events meeting criteria for a DLT will be treated as a DLT whether they occur after administration of the priming or the full dose.

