##### **6.2.1.4.1.2 Hematologic Dose-limiting Toxicity**

- Grade 3 CRS that does not resolve to  $\leq$  grade 1 within 72 hours or grade 4 CRS.
- Grade 3 TLS that does not resolve to  $\leq$  grade 1 within 72 hours or grade 4 TLS.
- Grade 4 neutropenia for  $> 5$  days or febrile neutropenia.
- Grade 3 thrombocytopenia with bleeding or grade 4 thrombocytopenia.
- Grade 4 anemia.
- Grade 5 adverse events.
- Lymphopenia will not be considered a DLT.

- Adverse events that require a delay in initiation of the next scheduled cycle by > 14 days.

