#### **8.1.2 Treatment Period**

Visits will occur per the Schedule of Activities (Section 1.3). On-study visits may be completed within the deviation window presented in the Schedule of Activities (Section 1.3). The date of the first dose of AMG 340 is defined as day 1. All subsequent doses and study visits will be scheduled based on the day 1 date. Administration of AMG 340 is to be administered last during each visit that it is required.

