**Table 11-1. Analyte Listing**

Local Laboratory: Chemistry	Local Laboratory: Coagulation	Local Laboratory: Urinalysis	Local Laboratory: Hematology	Other Lab Analytes
Sodium	PT/INR	Urobilinogen	RBC	Central Laboratory:
Potassium	PTT/aPTT	Blood	Hemoglobin	
Chloride		Protein	Hematocrit	
Bicarbonate		Glucose	MCV	
Total protein		Bilirubin	MCH	
Albumin		Microscopic examination	MCHC	
Calcium			Platelets	
Magnesium			WBC	
Glucose			NLR	
BUN or Urea			Differential	Local Laboratory:
Creatinine			• Bands/stabs	
Total bilirubin			Neutrophils (only %)	Serum or Urine
ALP			Eosinophils (if detected; absolute and %)	Pregnancy
LDH			Basophils (if detected; absolute and %)	Testosterone
AST (SGOT)			Lymphocytes (absolute and %)	Hep B surface antigen
ALT (SGPT)			Monocytes (absolute and %)	Hep C antibody
γ-glutamyl transferase				HIV Ab/Ag a
B2-microglobulin				
CRP				
Ferritin				
d-dimer				
Fibrinogen				
Urine telopeptide				

ALP = alkaline phosphatase; ALT = alanine aminotransferase; AST = aspartate aminotransferase;  
BUN = blood urea nitrogen; CRP = C-reactive protein; HDL = high density lipoprotein; Hep = hepatitis;  
HIV = human immunodeficiency virus; HLA = human leukocyte antigen; INR = international normalized ratio;  
LDH = lactate dehydrogenase; LDL = low density lipoprotein; MCH = mean corpuscular hemoglobin;  
MCHC = mean corpuscular hemoglobin concentration; MCV = mean corpuscular volume; NLR = neutrophil  
to lymphocyte ratio; [REDACTED] PT = prothrombin time; PTT = partial thromboplastin  
time; RBC = red blood cell count; RDW = red cell distribution width; SGOT = serum glutamic-oxaloacetic  
transaminase; SGPT = serum glutamic-pyruvic transaminase; WBC = white blood cell count  
a HIV assessment is recommended.

[figure not shown]
If the subject is being followed for possible drug induced liver injury (DILI), the following  
analytes may be tested at the local laboratory depending on the clinical situation (see  

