**Table 11-7. Cairo-Bishop Definition of Laboratory Tumor Lysis Syndrome**

Element	Value	Change from baseline
Uric acid	$\geq 476 \mu\text{mol/L}$ or 8 mg/dL	25% increase
Potassium	$\geq 6.0 \text{ mmol/L}$ or 6 mg/L	25% increase
Phosphorus	$\geq 2.1 \text{ mmol/L}$ for children or $\geq 1.45 \text{ mmol/L}$ for adults	25% increase
Calcium	$\leq 1.75 \text{ mmol/L}$	25% decrease

Note: Two or more laboratory changes within 3 days before or 7 days after cytotoxic therapy will constitute laboratory tumor lysis syndrome.

Clinical TLS requires the presence of laboratory TLS in addition to 1 or more of the following significant complications: renal insufficiency, cardiac arrhythmias/sudden death, and seizures. The grade of clinical TLS is defined by the maximal grade of the clinical manifestations as detailed in [Table 11-8](#).

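### The required chemistry panel omits uric acid and phosphorus, two of the four analytes that define tumor lysis syndrome, and the definition's 7-day window has two unreconciled anchors

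*Protocol*

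**What the plan says.** Protocol Table 2-2 lists TLS among the potential safety concerns: "Signs and symptoms may include hyperkalemia, hyperphosphatemia, hyperuricemia, hyperuricosuria, and hypocalcemia". Section 2.2.4.2.1 says that the Schedule of Activities "is designed to monitor and risk mitigate other known toxicities associated with previous bispecific CD3/PSMA therapies that include infections, tumor lysis syndrome". Section 6.2.1.4.1.2 makes TLS a DLT if it is grade 3 and does not improve to at most "grade 1 within 72 hours or grade 4 TLS".

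Section 11.11 adopts the Cairo-Bishop classification to define presence and grade, because CTCAE does not clearly define presence. Section 8.4.6.1.1 and SAP Section 9.6.2 follow it. The text reads: "laboratory TLS is defined as any 2 or more abnormal serum values present within 3 days before or 7 days after initiation of treatment". It adds that this is in the setting of adequate hydration and use of a hypouricemic agent. Table 11-7 gives a threshold value and a 25% change from baseline for each of uric acid, potassium, phosphorus and calcium. Its note counts the 7 days from cytotoxic therapy and does not mention a hypouricemic agent. Below it: "Clinical TLS requires the presence of laboratory TLS in addition to 1 or more of the following significant complications".

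Section 8.4.3 makes Section 11.2 the list of required laboratory tests. In Table 11-1, the column headed "Local Laboratory: Chemistry" includes potassium and calcium, but neither uric acid nor phosphorus. Table 11-2, for liver injury, has neither as well.

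On dosing, Section 8.1.2 makes the first dose day 1. Where priming is used, Section 6.2.1.2 says: "On Cycle 1 Day 8, subjects will receive the full dose corresponding to the cohort in which they have been enrolled".

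**The concern.** The TLS grade exists only if laboratory TLS has first been shown, and laboratory TLS needs two abnormal analytes out of four. If two of the four are not on the required list, a site that follows the protocol exactly can miss the classification. The DLT criterion and the TLS rows of Table 6-6 then have no grade to act on. The trial is first-in-human, and Section 2.2.4.2 says that no relevant animal species was available for toxicology. A low TLS count should therefore mean that TLS was looked for.

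The window raises a second question. If the 7 days run from the first dose, step dosing may place the first full dose at the very end of the period in which laboratory changes count.

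**Working it through.** The plan states no figure on this point, so the check is by enumeration and by counting days.

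**Analytes.** Inputs: four elements (Table 11-7), of which two, potassium and calcium, are on the legible required list (Table 11-1).

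- Qualifying pairs: C(4,2) = 6. Pairs available from required tests: C(2,2) = 1 (potassium with calcium).
- Patterns with at least two abnormal elements: 6 + 4 + 1 = 11. Patterns that required tests can recognize need both potassium and calcium abnormal, with the other two free: 2 × 2 = 4.
- If a site also measures phosphorus: C(3,2) = 3 of 6 pairs.
- With all four measured: 6 of 6 pairs and 11 of 11 patterns.

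These are counts of combinations. They are not detection probabilities, because the documents give no frequencies for the patterns.

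**Baseline.** SAP Section 5.3 takes the last value at or before the cycle 1 day 1 pre-dose assessment as baseline. No uric acid or phosphorus value is required by then. A test ordered later, on suspicion, may have nothing against which to compute a 25% change.

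**Window.** Cycle 1 chemistry days in Table 1-1 are 1, 2, 3, 5, 8 and 15, plus 6 and 7 if a day 5 priming dose is used, and 9 and 10 if day 8 is dosed.

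| Case | Window ends | Draws on days after the full dose that fall inside |
|---|---|---|
| Primed, counted from start of treatment | 1 + 7 = day 8 | none of days 9, 10, 15 |
| Primed, counted from the day 8 dose | 8 + 7 = day 15 | days 9, 10, 15 |
| Unprimed, full dose on day 1 | 1 + 7 = day 8 | days 2, 3, 5, 8 |

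The second row is one possible reading of the Table 11-7 note. The protocol does not say whether AMG 340 counts as cytotoxic therapy, or which dose starts the clock. Under the first row, days 9 to 21 of the 21-day DLT period (21 − 8 = 13 days) follow the close of the window. Priming matters for the current regimen: Section 2.2.4.3 reports that it was triggered in cohort 5.

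The day 8 sample itself is uncertain. Section 8.1.2 says: "Administration of AMG 340 is to be administered last during each visit that it is required". That suggests a pre-dose draw. But vital signs are taken for hours after the day 8 infusion, and the chemistry row carries a footnote (e) whose text is not in the public version.

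**Handling.** In Table 6-6, grade 2 clinical TLS requires interruption and grade 3 or higher requires permanent discontinuation. The row for other AMG 340-related events starts at grade 3, covers events not meeting DLT criteria, and allows restart. The label therefore changes which instructions apply.

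**The case against.** The best case for the plan has four parts.

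- **Practice may be better than the list.** Section 11.2 allows additional tests at the investigator's judgment. Section 2.2.4.3 reports hypophosphatemia in 5 of 23 subjects, so phosphorus was measured in some. This stands, and it rules out saying that TLS cannot be detected. It does not cure the gap: such testing is discretionary, it secures no baseline, and it says nothing about uric acid.
- **The list may be incomplete as published.** The Central Laboratory entries in Table 11-1 and Schedule of Activities footnote e are not legible. This stands as a limit. The local chemistry column, where these analytes would be expected, is legible.
- **Severe events are still caught.** Section 6.2.1.4.1.1 makes most non-hematologic events of grade 3 or higher DLTs, so a severe renal, cardiac or seizure event may count without the TLS label. The TLS criterion exempts grade 3 TLS that resolves within 72 hours, so losing the label could even add a DLT. This largely stands. A reader might infer that DLTs would be undercounted; the documents do not support that as a general result.
- **The window is ambiguous and does not clearly exclude anything.** A reader might infer that TLS after the first full dose is excluded by definition. That holds only for primed subjects and only if the clock runs from the start of treatment. The Table 11-7 note permits another reading, and unprimed subjects have several draws after the full dose inside the window. The same note also classifies without the hypouricemic agent, so its absence does not clearly block classification.

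Section 2.2.4.3 lists no TLS among the frequent, grade 3 or higher, or serious events in 23 treated subjects. With uric acid not on the required list, that is limited reassurance.

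**Conclusion.** The concern holds in this form. A protocol-defined DLT depends on four analytes, and the legible required list contains two. Required tests alone can establish laboratory TLS through 1 of 6 pairs (4 of 11 patterns), and no baseline is secured for the other two analytes. What is lost is mainly TLS classification and the matching Table 6-6 handling. A zero TLS count would partly reflect what was not required to be measured.

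Separately, Section 11.11 and the Table 11-7 note disagree on the window anchor and on the hypouricemic-agent condition. Neither is tied to the priming schedule or to the DLT period. The day 8 closure is a consequence of one anchor, in primed subjects only.

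This rests on two assumptions: that the illegible laboratory entries do not contain uric acid or phosphorus, and that sites may limit themselves to required tests.

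**What to change.** 1. Add uric acid and phosphorus to the Table 11-1 chemistry panel, so that they run at every existing chemistry draw, including screening and pre-dose day 1. All 6 pairs then become assessable and a baseline exists. If either analyte is already in the illegible entries, say so in the chemistry column.
2. Reconcile the Section 11.11 text with the Table 11-7 note on the window anchor and on whether a hypouricemic agent is a condition. Reconcile both with the priming schedule in Section 6.2.1.2 and the 21-day DLT period in Section 6.2.1.4.1. The choice of rule drives interruption and discontinuation and belongs to the sponsor. What is needed is one stated rule.

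The cost is two additional analytes at draws already scheduled, plus appendix wording. The downside is a few more isolated laboratory abnormalities to review.
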